Appendix D: BMT 29 Schedule of Assessments

Study Period	Screening	Treatment Period							Follow-Up		
		Cycle 1				Cycles 2 to 6	Cycle 7	Cycles 8+			
Cycle ^a											
Visit Day	Day -28 to -1 ^b	1	8	15	22	1 (± 7 days)	1 (± 7 days)	1 (± 7 days)		(± 7 days)	Every 3 months (± 1 month)
Informed consent	X										
Inclusion / exclusion criteria	X										
Medical history and demographics ^c	X										
Physical examination ^{c,d}	X	X	X	X	X	X	X	X	X	X	
ECOG performance status ^{c,d}	X	X				X	X	X	X	X	
Vital signs ^c	X	X	X	X	X	X	X	X	X	X	
Blood transfusion review ^d	X	X				X	X	X	X		
12-Lead electrocardiogram ^c	X								X		
Pulmonary function test ^d	X					X (C4 only)	X				
Urine pregnancy test ^{c,e}	X	X				X	X	X	X	X	
Safety laboratory (hematology, lipids [fasting], and chemistries) ^c	X	X	X	X	X	X	X	X	X	X	
Safety laboratory (urine) ^c	X	X	X	X	X	X	X	X	X	X	
Virology testing ^f	X										
Concomitant medication review	X	X	X	X	X	X	X	X	X	X	
Adverse events and infection monitoring	X	X	X	X	X	X	X	X	X	X	
cGVHD diagnosis and staging	X										
Clinician-reported global cGVHD activity assessment ^g		X				X	X	X	X		

CONFIDENTIAL

INNOVATIONS STUDY NUMBER: BMT 29

VERSION 4

STUDY DRUG: INCB039110 (ITACITINIB)
FINAL PROTOCOL DATE: 26 OCTOBER 2021

Study Period	Screening	Treatment Period						Follow-Up		
		Cycle 1			Cycles 2 to 6	Cycle 7	Cycles 8+	EOT ^k	30-Day Safety FU ^l	FU for Survival ^m
Cycle ^a		1	8	15	22	1 (± 7 days)	1 (± 7 days)	1 (± 7 days)	(± 7 days)	Every 3 months (± 1 month)
Visit Day	Day -28 to -1 ^b									
Patient-reported global cGVHD activity assessment ^g		X				X	X	X	X	
Assessment of cGVHD response (NIH criteria) ^h						X	X	X ^h	X	
Chimerism assessment (institutional standards)	X									
Lee Symptom Scale ⁱ	X	X					X		X	
Document corticosteroid dosage (total dose/kg and type of corticosteroid)	X	X	X	X	X	X	X	X	X	
Document concomitant cGVHD therapies	X	X	X	X	X	X	X	X	X	
Assess underlying disease relapse ^j		X				X	X	X	X	X
New cGVHD therapies										X X
Dispense/collect study drug		X				X	X	X	X	
Patient status										X

Itacitinib Schedule of Assessments Footnotes

- a Treatment cycles are 28 days (4 weeks). Patients will continue treatment with itacitinib for up to 24 months or until patients discontinue from study treatment for any of the following reasons listed in Section 3.3.
- b Screening should take place within 28 days of start of study treatment.
- c Safety laboratory assessments including hematology, lipids (fasting), clinical chemistry, pregnancy test, and urinalysis will be performed locally. Additional assessments to be performed during the screening period:
 - Blood transfusion review
 - Virology tests (HIV, Hepatitis B surface antigen, Hepatitis B surface antibody, Hepatitis B core antibody, Hepatitis C antibody, HBV-DNA [if required], HCV-RNA [if required])

CONFIDENTIAL

INNOVATIONS STUDY NUMBER: BMT 29

VERSION 4

- Concomitant medication review
- cGVHD diagnosis and staging
- Chimerism assessment as per institutional standards
- Lee Symptom Scale
- Document corticosteroid dosage (total dose/kg and type of corticosteroids)
- Document concomitant cGVHD therapy

The following screening parameters should be done \leq 14 days prior to initiation of treatment:

- Pulmonary function tests (FEV1, FVC, DLCO (corrected for Hb), TLC and RV)
- medical history and demographics (includes conditioning regimen, stem cell source, GVHD prophylaxis therapy, disease status at transplant and prior lines of GHVD therapy), physical examination (including height and weight), Eastern Cooperative Oncology Group (ECOG) performance status, vital signs, electrocardiogram (ECG)
- **hematology:** hematocrit, hemoglobin, mean corpuscular volume, platelet count, red blood cell count, white blood cell (WBC) count, WBC 5-part differential
- **clinical chemistry (lipids in a fasting state):** sodium, potassium, phosphorus, chloride, creatinine, calcium, venous bicarbonate, albumin, total protein, aspartate aminotransferase (AST), alanine aminotransferase (ALT), alkaline phosphatase (ALP), total bilirubin, lactate dehydrogenase, serum glucose, and blood urea nitrogen, lipids high-density lipoprotein (HD) cholesterol, low-density lipoprotein (LDL) cholesterol, total cholesterol, and triglycerides
- **urinalysis**
- screening pregnancy test (urine)

If these assessments are performed within 72 hours of initiation of treatment, they do not need to be repeated on Cycle 1 Day 1 with the exception of the ECOG performance status, an abbreviated physical examination, and vital signs, which are required prior to first study dose. Vital signs (blood pressure, body temperature, and pulse rate) are checked at every visit prior to blood work and study treatment and at the discretion of the Investigator (see Section 6.7.3).

- d Physical examinations including the measurements of height (screening only) and weight will be done at screening, on Days 1, 8, 15, and 22 of Cycle 1, on Day 1 of each subsequent treatment cycle, at the end-of-treatment (EOT) and the 30-day safety follow-up (FU) visits, and at the discretion of the Investigator. Blood transfusions will be reviewed at screening, on Day 1 of each cycle, and at the EOT visit. ECOG performance status will be done at the visits noted in the table. Pulmonary function test will be performed at screening (within 14 days of C1D1) and on Day 1 of Cycle 4 and Cycle 7 and include FEV1, FVC, DLCO (corrected for Hb), TLC and RV (see Section 6.7.3).
- e A urine pregnancy test must be done at screening (3 days prior to initiation of treatment) for women with child-bearing potential, Day 1 of each cycle, at the EOT visit, and at the 30-day safety follow-up visit. Additional pregnancy testing is at the Investigator's discretion. Positive results are to be confirmed with serum beta human chorionic gonadotropin testing.

CONFIDENTIAL

INNOVATIONS STUDY NUMBER: BMT 29

VERSION 4

- f Virology tests to include: HIV, Hepatitis B surface antigen, Hepatitis B surface antibody, Hepatitis B core antibody, Hepatitis C antibody, HBV-DNA (if required), HCV-RNA (if required)
- g Patients will be assessed for severity of cGVHD using the Clinician-Reported Global cGVHD Activity Assessment Form (see Appendix E) and Patient-reported cGVHD Activity Assessment Form (Appendix F) on Day 1 of each cycle, and at the EOT visit. If a patient withdraws from treatment due to reasons other than PD, GVHD grading will be repeated at this visit.
- h Response criteria (CR, PR, or progression) based on the 2014 NIH Consensus Development Project on Clinical Trials in cGVHD (see Appendix H for criteria) will be assessed on Day 1 of Cycles 2 through 7; and then every odd-numbered cycle thereafter starting on Day 1 of Cycle 9, as well as the EOT visit.
- i The Lee Symptom Scale (see Appendix I) will be used to capture changes in health status during the course of treatment relative to screening and will be done at screening, on Cycle 1 Day 1, Cycle 7 Day 1, and at the EOT visit. If a patient stops study drug before 6 months, the form should be filled out at that time.
- j Participants will be closely monitored for any evidence of underlying disease relapse or recurrence on Day 1 of each cycle, at the EOT, and the survival follow-up visit. A formal re-staging is not required. Re-staging will be done at the Investigator's discretion. The date of malignant and non-malignant hematologic disease relapse and subsequent management should be collected on the appropriate eCRF.
- k An EOT visit should be performed for all patients who permanently discontinue study treatment (preferably within 7 days and no later than 14 days after the last treatment of study drug). If the EOT visit coincides with a regular study visit, the EOT evaluations will supersede those of that scheduled visit, and the data should be entered in the EOT visit in the eCRF (see Section 6.5).
- l A safety follow-up visit will be done 30 days (± 7 days) following end of treatment. Adverse events and SAEs must be reported for least 30 days after the last dose of study drug, and must be followed until toxicities resolve, return to baseline, or are deemed irreversible, whichever is longer (see Section 6.6.1).
- m Follow-up for survival: patients will be followed for survival after treatment has been discontinued. Patients should be contacted by telephone, email, or visit every 3 months for 1-year after their last dose of study treatment to assess for new GVHD therapy, relapse of underlying malignancy and survival status until death, withdrawal of consent, or the end of the study, whichever occurs first (see Section 6.6.2).

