3.3 Discontinuation from Study Treatment

Patients will be discontinued from study treatment for any of the following reasons:

- Relapse of underlying malignancy
- Irreversible or intolerable toxicity or abnormal laboratory values thought to be related to drug toxicity
- The patient is unable to tolerate itacitinib at a dose of 100 mg QD.
- Additional systemic therapy is required for GVHD progression or lack of response, including corticosteroid doses greater than those used on Study Day 1.
- Conditions requiring therapeutic intervention not permitted by the protocol
- Intercurrent illness (this will be at the Investigator's discretion)
- Inability of the patient to comply with study requirements
- Patient requests to discontinue treatment, but agrees to finish study procedures
- Patient withdraws consent from the study and is discontinued from the study
- Non-compliance/lost to follow-up
- Pregnancy
- Further participation would be injurious to the patient's health or well-being, in the Investigator's medical judgment.
- The study is terminated by the Sponsor or the Institutional Review Board (IRB).

After discontinuation from protocol treatment, patients must be followed for AEs for 30 days after their last dose of study drug. All new AEs occurring during this period must be reported and followed until resolution, unless, in the opinion of the Investigator, these values are not likely to improve, because of the underlying disease. In this case, the Investigator must record his or her reasoning for this decision in the patients' medical records.

All patients who have Grade 3 or 4 laboratory abnormalities (per National Cancer Institute Common Terminology Criteria for Adverse Events [NCI CTCAE] Version 5) at the time of discontinuation must be followed until the laboratory values have returned to Grade 1 or 2, unless it is, in the opinion of the Investigator, not likely that these values will improve. In this case, the Investigator must record his or her reasoning for making this decision in the patients' medical records.

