6.6 Follow-up

6.6.1 Safety Follow-Up (30 [\pm 7] Days Following Last Dose of Study Treatment)

A 30-day safety follow-up assessment will be performed after the last dose of itacitinib.

The following assessments will be performed at this visit:

- Physical examination
- ECOG performance status
- Vital signs (blood pressure, body temperature, and pulse rate after about 5 minutes of rest)
- Hematology, lipid (fasting), and clinical chemistry panels
- Urinalysis
- Urine pregnancy test for women of child-bearing potential
- Concomitant medication review
- AE and infection monitoring
- Discuss new GVHD therapies

CONFIDENTIAL

STUDY DRUG: INCB039110 (ITACITINIB)
FINAL PROTOCOL DATE: 26 OCTOBER 2021

INNOVATIONS STUDY NUMBER: BMT 29
VERSION 4

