11.1.5.2 Reporting Period for Adverse Events

All AEs regardless of seriousness or relationship to the study treatment spanning from the signing of the informed consent form until 30 calendar days after discontinuation or completion of study treatment, as defined by this clinical study protocol, are to be recorded on the corresponding screen(s) included in the eCRF.

All AEs resulting in discontinuation from the study should be followed until resolution or stabilization. All new AEs occurring during this period must be reported and followed until resolution unless, in the opinion of the Investigator, the AE or laboratory abnormality/ies are not likely to improve because of the underlying disease. In this case, the Investigator must record his or her reasoning for this decision in the patient's medical record.

After 30 days of completion of protocol-specific treatment or discontinuation, only AEs, SAEs, or deaths assessed by the Investigator as treatment-related are to be reported.

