Appendix C: Guidelines for Female Patients of Childbearing Potential and Fertile Male Patients

Acceptable Contraception Methods:

Women of childbearing potential, defined as all women physiologically capable of becoming pregnant, must use highly-effective contraception during the study and until after the 30-day safety follow-up visit.

Highly effective contraception is defined as either:

True Abstinence	When this is in line with the preferred and usual lifestyle of the patient. Periodic abstinence (e.g., calendar, ovulation, symptothermal, post-ovulation methods) and withdrawal are not acceptable methods of contraception.
Sterilization	When a woman of childbearing potential has had surgical bilateral oophorectomy (with or without hysterectomy) or tubal ligation at least 6 weeks prior to study entry. In case of oophorectomy alone, only when the reproductive status of the woman has been confirmed by follow-up hormone level assessment.
Male Partner Sterilization	When the appropriate post-vasectomy documentation of the absence of sperm in the ejaculate.

Use of a combination of any 2 of the following (one from a + one from b):

- a) Placement of an intrauterine device (IUD) or intrauterine system (IUS)
- b) Barrier methods of contraception: Condom or Occlusive cap (diaphragm or cervical/vault caps) with spermicidal foam/gel/film/cream/vaginal suppository.

Fertile male patients, defined as all males physiologically capable of conceiving offspring, with female partners of childbearing potential must use condoms plus a spermicidal agent during the study treatment period and until after the 30-day safety follow-up visit, and must not father a child during this period.

Male patients must also refrain from donating sperm during their participation in the study and for at least 3 months after completing the study.

The following are acceptable forms of barrier contraception:

- Latex condom, diaphragm or cervical/vault cap when used with spermicidal foam/gel/film/cream/suppository

Unacceptable Contraception Methods: for women of childbearing potential include:

- IUD progesterone T
- Female condom

CONFIDENTIAL

STUDY DRUG: INCB039110 (ITACITINIB)
FINAL PROTOCOL DATE: 26 OCTOBER 2021

INNOVATIONS STUDY NUMBER: BMT 29
VERSION 4

- Natural family planning (rhythm method) or breastfeeding
- Fertility awareness
- Withdrawal
- Cervical shield.

Pregnancies

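### The closing safety visit may be held up to 7 days before the 30-day adverse event period ends, and no later scheduled contact asks about adverse events.

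*Combined protocol and SAP*

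**What the plan says.** **Visit.** Section 6.6.1 carries a 30 ± 7 day window in its heading and counts from the last dose: "A 30-day safety follow-up assessment will be performed after the last dose of itacitinib". Appendix D repeats the ± 7 days in its column header and again in footnote l: "A safety follow-up visit will be done 30 days (± 7 days) following end of treatment".

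**AE collection.** The next sentence of footnote l sets a minimum: "Adverse events and SAEs must be reported for least 30 days after the last dose of study drug". Section 3.3 says that "patients must be followed for AEs for 30 days after their last dose of study drug". Section 11.1.5.2 records all AEs, whatever their seriousness or cause, "until 30 calendar days after discontinuation or completion of study treatment". Sections 6.7.11 and 11.2 give the same 30 days. After that point, under Section 11.1.5.2, "only AEs, SAEs, or deaths assessed by the Investigator as treatment-related are to be reported".

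**Neighbouring contacts.** The end-of-treatment (EOT) visit is to be held within 7 days, and no later than 14 days, after treatment stops (Section 6.5; Appendix D, footnote k). Survival follow-up is every 3 months, ± 30 days in Section 6.6.2, and covers survival, relapse and new cGVHD therapy. In Appendix D the AE row is marked from screening through the 30-day visit and is not marked under survival follow-up.

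**The concern.** The visit window and the AE period are both centred on Day 30, but the visit may come before Day 30 and the AE period may not end before it. A site that sees a patient on Day 23 has followed the protocol, yet nothing scheduled afterwards asks the patient about the days up to Day 30.

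Safety and tolerability is a secondary objective, assessed in Section 10.4.3 through the incidence of treatment-emergent AEs. That definition gives a start (first treatment) but no end date, so incidence depends partly on how long each patient was actually asked, and the visit window lets that time vary with booking. Section 1.2 names infection as a possible consequence of itacitinib and calls for close monitoring. An event on Days 24 to 30 that the investigator judges unrelated is required data, but no later scheduled contact would elicit it.

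**Working it through.** The plan gives no figure of its own on this point, so the check is calendar arithmetic with the last dose as Day 0.

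**Inputs**
- Visit window: 30 ± 7 days (Section 6.6.1; Appendix D header and footnote l).
- AE period: to at least Day 30 (Sections 3.3, 6.7.11, 11.1.5.2 and 11.2; footnote l).
- Latest EOT visit: Day 14 (Section 6.5; footnote k).
- First survival contact: 3 months ± 30 days (Section 6.6.2). Taking 3 months as 91 days, this is Day 61 to Day 121.

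**Step 1: permitted visit days.** 30 − 7 = 23 and 30 + 7 = 37, so Days 23 to 37, which is 15 days.

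**Step 2: days without a scheduled AE enquiry.** For a visit on day *d*, the gap is max(0, 30 − *d*).

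| Visit day | 23 | 24 | 25 | 26 | 27 | 28 | 29 | 30 to 37 |
|---|---|---|---|---|---|---|---|---|
| Gap (days) | 7 | 6 | 5 | 4 | 3 | 2 | 1 | 0 |

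The largest gap is 7 days (Days 24 to 30), and 7/30 = 23% of the period.

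**Step 3: can another contact fill the gap?** The EOT visit ends by Day 14, before the gap opens. The first survival contact comes at about Day 61 at the earliest and has no AE assessment. For patients on that path, nothing scheduled fills it.

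**Step 4: average size, assuming visits spread evenly over the 15 permitted days.** The documents do not give the actual distribution.
- Share of visits before Day 30: 7/15 = 47%.
- Sum of gaps: 7 + 6 + 5 + 4 + 3 + 2 + 1 = 28 days.
- Mean over all patients: 28/15 = 1.9 days.
- Mean over early visits only: 28/7 = 4 days.

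If every visit were on Day 30 or later, the mean would be 0. If every visit were on Day 23, it would be 7 days.

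**Step 5: does the anchor matter?** Footnote l counts from the end of treatment and Section 6.6.1 from the last dose. If footnote l meant the EOT visit, held on day *e*, the earliest safety visit would be Day *e* + 23 and the largest gap max(0, 7 − *e*).
- *e* = 0: window Day 23 to 37, gap up to 7 days.
- *e* = 7: window Day 30 to 44, no gap.
- *e* = 14: window Day 37 to 51, no gap.

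That reading removes the gap only when the EOT visit is at least 7 days after the last dose. Footnote l itself points to Section 6.6.1, which uses the last dose.

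**Step 6: after the fix.** With a window of Day 30 to Day 37, the largest gap is max(0, 30 − 30) = 0.

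**The case against.** The strongest reply is that both rules can be followed together, because the duty to report does not depend on the visit. SAEs must be notified within 24 hours of first knowledge, whatever the cause (Section 11.2). Volunteered AEs count (Section 11.1.6), and open AEs are followed further (Sections 3.3 and 11.1.5.2). An event with onset by Day 30 that is learned of later is still recordable. Treatment-related events stay reportable after Day 30, and new cGVHD therapy is recorded through survival follow-up, so flares that need new treatment remain visible. All of this stands. A reader might infer that the last week has no contact or is unobserved. The documents support only that it may have no *scheduled* AE enquiry.

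A second reply is that the gap is small. Against roughly a year of treatment plus 30 days, the worst case is 7/(365 + 30) = 1.8% of AE observation, and more for patients who stop early. The safety analysis is descriptive, in one arm of up to 40 patients. This also stands, and it limits the weight of the point.

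A third reply is that the gap does not reach everyone. Under Section 5.1, patients who taper off study drug and all immunosuppression in complete or partial response remain on the Appendix D schedule, with all safety assessments. They may have other visits in the interval.

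A reader might also infer that an early visit cuts short a 30-day contraception period. The documents do not support this. Appendix C says that women "must use highly-effective contraception during the study and until after the 30-day safety follow-up visit", and Inclusion Criterion 11 likewise ends the precaution at the safety follow-up. The end point is the visit, and no separate number of days is stated. The end of contraception and the last pregnancy test move with the visit, but no contradiction is claimed there.

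**Conclusion.** The point holds as a minor gap in ascertainment. A compliant visit on Days 23 to 29 leaves 1 to 7 of the 30 mandatory days without a scheduled AE enquiry, and those days rest on unsolicited reports. The 1.9-day mean over all patients rests on an assumed even spread of visits. The 47% share of early visits rests on the same assumption. The 4-day mean describes early visits only and should not be read as the expected loss per patient.

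The conclusion assumes that the visit is counted from the last dose, as in Section 6.6.1, and that the patient is not still on Appendix D treatment-period visits. The possible consequence is some under-recording of late AEs, mainly those judged unrelated, and AE observation time that varies with booking. The primary response rate is not affected.

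**What to change.** Make the visit window one-sided in Section 6.6.1, the Appendix D column header and footnote l: Day 30 to Day 37 after the last dose. Use the last dose as the anchor in all three places. The largest gap then falls from 7 days to 0, with the same visit and the same tests. The cost is less scheduling flexibility (8 permitted days instead of 15) and a wording change through the amendment process.

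If early visits must be kept, a telephone AE enquiry on or after Day 30 for those patients would also close the gap. That adds a procedure, and Section 14.1 lists added procedures among the changes that need amendment approval.

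Because the last pregnancy test and the end of contraception are tied to this visit, the sponsor should note that they move with it. No other change to that text is asked for here.

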Appendix E: Clinician-Reported Global cGVHD Activity Assessment Form

Appendix: Clinician -Reported Global cGVHD Activity Assessment Form

BMT29

Current Patient Weight: _____
Today's Date: _____
Cycle#/Visit #: _____

Subject ID#:

CHRONIC GVHD ACTIVITY ASSESSMENT- CLINICIAN

STUDY DRUG: INCB039110 (ITACITINIB)
FINAL PROTOCOL DATE: 26 OCTOBER 2021

CONFIDENTIAL

INNOVATIONS STUDY NUMBER: BMT 29
VERSION 4

Lungs (Liters and % predicted) • Bronchiolitis Obliterans	FEV1	FVC	Single Breath DLCO (adjusted for hemoglobin)		TLC	RV
Liver Values	Total serum bilirubin mg/dL	ULN mg/dL	ALT U/L	ULN U/L	Alkaline Phosphatase U/L	ULN U/L
Baseline Values	Total Distance Walked in 2 or 6 Mins:  2 min  6 min		Karnofsky or Lansky	PlateletCount K/uL	Total WBC K/uL	Eosinphils %
 Abnormality present but explained entirely by non-GVHD documented cause (specify site/alternate cause): _____  Abnormality present but explained entirely by non-GVHD documented cause (specify site/alternate cause): _____  Abnormality present but explained entirely by non-GVHD documented cause (specify site/alternate cause): _____						

Reference: Lee et al. 2015

STUDY DRUG: INCB039110 (ITACITINIB)
FINAL PROTOCOL DATE: 26 OCTOBER 2021

CONFIDENTIAL

INNOVATIONS STUDY NUMBER: BMT 29
VERSION 4

CHRONIC GVHD ACTIVITY ASSESSMENT- CLINICIAN

[figure not shown]
CONFIDENTIAL

STUDY DRUG: INCB039110 (ITACITINIB)
FINAL PROTOCOL DATE: 26 OCTOBER 2021

INNOVATIONS STUDY NUMBER: BMT 29
VERSION 4

	SCORE 0	SCORE 1	SCORE 2	SCORE 3
LUNGS	 No symptoms	 Mild symptoms (shortness of breath after climbing one flight of steps)	 Moderate symptoms (shortness of breath after walking on flat ground)	 Severe symptoms (shortness of breath at rest; requiring O ₂)
Abnormality present but explained entirely by non-GVHD documented cause (specify): _____				
JOINTS AND FASCIA	 No symptoms	 Mild tightness of arms or legs, normal or mild decreased range of motion (ROM) AND not affecting ADL	 Tightness of arms or legs OR joint contractures, erythema thought due to fasciitis, moderate decrease ROM AND mild to moderate limitation of ADL	 Contractures WITH significant decrease of ROM AND significant limitation of ADL (unable to tie shoes, button shirts, dress self etc.)
□ Abnormality present but explained entirely by non-GVHD documented cause (specify): _____				

All abnormalities should be documented; however, the organ is not evaluable if there is another well-documented non-chronic GVHD cause.

Reference: Lee et al. 2015

CONFIDENTIAL

STUDY DRUG: INCB039110 (ITACITINIB)
FINAL PROTOCOL DATE: 26 OCTOBER 2021

INNOVATIONS STUDY NUMBER: BMT 29
VERSION 4

